### 9.5.4 Analysis of Exploratory Endpoints

**Metabolic and physiologic imaging parameters:** We will determine if metabolic and physiologic imaging parameters correlate with the clinical endpoints of time to progression and survival. We will assess the usefulness of these parameters in predicting PFS and OS using Cox regression. If the number of patients with responses is sufficient we will also assess the ability of the imaging score to predict response using logistic regression. In addition to the imaging parameters, the models will include: age, KPS, extent of resection, time since diagnosis, Arm 1, 2 vs. 3, and initial diagnostic histology scored as oligodendrogloma only vs. those with an astrocytoma component. The inclusion of these additional variables is to adjust for known or potential confounding risk factors.

**Clonal or subclonal genetic mutations:** We will assess the association between the presence/absence of clonal or subclonal genetic mutations in the PI3K pathway and median PFS, Objective Response Rate (ORR), *PTEN* methylation, and the immunohistochemical measurements of the PI3K pathway activation in patients together and by arm. Tests for association will be used as appropriate including chi-square for proportions and contingency tables and t-tests for continuous valued variables.

**Quality of Life Parameters:** Data from the end of 12 cycles of therapy, the end of 24 cycles of therapy, and one year post-therapy will be compared to baseline data (at study enrollment) to see if there are consistent temporal trends between patients over time in total scores as well as in specific functional domains. Paired T-Tests will be employed to make these comparisons. In addition, variability analyses using all available timepoints will be undertaken to evaluate trends within single patients over time, for total scores as well as specific functional domains.

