##### **Exploratory objectives**

- 1) Pending adequate funding, to assess the ability of metabolic and physiologic imaging parameters such as MR spectroscopy, perfusion-weighted imaging, and diffusion-weighted imaging to predict clinically relevant endpoints such as time to progression and survival.
- 2) To assess for an association between the presence/absence of clonal or subclonal genetic mutations in the PI3K pathway and Median PFS, Objective Response Rate (ORR), *PTEN* methylation, and the immunohistochemical measurements of the PI3K pathway activation in patients treated with everolimus or TMZ and everolimus.
- 3) To longitudinally assess quality of life (QoL) in low-grade glioma patients over the course of treatment with everolimus (Arms 1 & 3).

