## 7.2.2 Imaging Time Points

Standard anatomic MR imaging will be performed as outlined in Table 7. The full imaging examination described above will optionally be performed at baseline, at the end of cycles 2 and 6, and at the time of suspected progression. The anatomic imaging components are standard of care, with the other parts being research add-ons. After the end of treatment and prior to progression, patients will be followed with anatomic imaging alone. The goal will be to determine whether the parameters estimated from advanced imaging are early predictors of response to therapy.

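### The imaging Cox models test several unspecified parameters and judge them in the same patients, with no multiplicity control or optimism correction, so imaging measures of no value can look predictive.

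*Combined protocol and SAP*

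**What the plan says.** Section 9.5.4 of the combined protocol and SAP sets the method: "We will assess the usefulness of these parameters in predicting PFS and OS using Cox regression". It then lists the covariates: "In addition to the imaging parameters, the models will include: age, KPS, extent of resection, time since diagnosis, Arm 1, 2 vs. 3", and as the sixth, "initial diagnostic histology scored as oligodendrogloma only vs. those with an astrocytoma component".

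The imaging side is open-ended. The exploratory objectives in Section 3 refer to "metabolic and physiologic imaging parameters such as MR spectroscopy, perfusion-weighted imaging, and diffusion-weighted imaging to predict clinically relevant endpoints", which names three modalities as examples. Section 7.2.2 gives the time points and makes the scans voluntary: "The full imaging examination described above will optionally be performed at baseline, at the end of cycles 2 and 6", with a further examination at suspected progression. The objective also depends on money: "Pending adequate funding, to assess the ability of metabolic and physiologic imaging parameters".

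Section 9.5.4 does not give the number of parameters, the time point to be used, whether parameters enter together or singly, or the statistic by which usefulness is judged. It plans no multiplicity adjustment, penalisation, cross-validation or bootstrap. The only condition on numbers is attached to the logistic model for response, which is fitted only if there are enough responders, with no threshold given. The PFS and OS models have no such condition.

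**The concern.** A claim of prediction needs two protections that this plan lacks. The first is control over how many parameters, time points and outcomes are tried. The second is an assessment of predictive value that is not made on the data used for fitting. Without the first, the chance that something reaches significance grows with the number of tests. Without the second, adding noise variables to a Cox model raises apparent discrimination, and more so when events are few for the number of terms.

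Section 7.2.2 states the aim as finding early predictors of response to therapy. A chance finding could therefore be carried into later work as an imaging marker.

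**Working it through.** **Plan's own figures.** Section 9.5.1: 105 patients at 2 per month is 105/2 = 52.5, so 53 months, and 53 + 38 = 91 months. Both reproduce. Section 9.3: with 35 patients and success at 22 or more progression-free, the exact binomial gives a one-sided error of 0.088 at 50% and power of 0.865 at 70%, which matches the stated 86%. The documents give no event count for the imaging models, so it has to be derived.

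**PFS events by month 91.** Inputs: 35 patients per arm (Section 5), PFS of 50% or 70% at 33 months (Arms 1 and 2) or 38 months (Arm 3), uniform accrual over 53 months. Assumption: exponential PFS. Follow-up runs from 38 to 91 months, so with hazard λ

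P(event) = 1 − (e^(−38λ) − e^(−91λ)) / (53λ).

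- 50% PFS: λ = 0.6931/33 = 0.02100 gives 0.728; λ = 0.6931/38 = 0.01824 gives 0.679. Events = 70 × 0.728 + 35 × 0.679 ≈ 75.
- 70% PFS: λ = 0.3567/33 = 0.01081 gives 0.495; λ = 0.3567/38 = 0.00939 gives 0.449. Events = 70 × 0.495 + 35 × 0.449 ≈ 50.
- If half are imaged, about 25 to 37.

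If MRI follow-up ends near month 58, the full-cohort figures are 45 to 69. OS events cannot exceed PFS events at the same cut-off, because death without progression counts as a PFS event (Section 9.1).

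**Simulation with null imaging parameters.** Six adjusters with modest real effects (assumed hazard ratios 0.6 to 1.35) and k independent imaging parameters with no effect, entered jointly. There were 1000 runs per row (2000 for k = 1). New-patient figures come from 1000 fresh patients per run.

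| Imaged / PFS events | k | Each parameter significant | At least one significant | C-index, same patients: clinical → with imaging | C-index, new patients |
|---|---|---|---|---|---|
| 105 / 75 | 1 | 6.4% | 6.4% | 0.658 → 0.662 | 0.623 → 0.620 |
| 105 / 75 | 3 | 5.6% | 15.5% | 0.659 → 0.668 | 0.622 → 0.615 |
| 105 / 75 | 5 | 6.5% | 28.3% | 0.660 → 0.675 | 0.622 → 0.610 |
| 105 / 75 | 8 | 7.8% | 46.7% | 0.656 → 0.681 | 0.622 → 0.602 |
| 105 / 50 | 3 | 6.0% | 16.7% | 0.669 → 0.681 | 0.618 → 0.609 |
| 105 / 50 | 5 | 6.5% | 27.1% | 0.670 → 0.691 | 0.618 → 0.603 |
| 105 / 50 | 8 | 7.6% | 43.8% | 0.666 → 0.699 | 0.617 → 0.593 |
| 52 / 26 | 1 | 6.4% | 6.4% | 0.690 → 0.698 | 0.602 → 0.597 |
| 52 / 26 | 3 | 7.6% | 20.3% | 0.692 → 0.714 | 0.602 → 0.588 |
| 52 / 26 | 5 | 9.2% | 35.7% | 0.688 → 0.728 | 0.599 → 0.577 |
| 52 / 26 | 8 | 11.0% | 54.6% | 0.690 → 0.751 | 0.601 → 0.569 |

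A separate simulation with cut-off at month 91 and 4 to 8 parameters agrees:

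- All 105 imaged (about 51-74 events): 7-8% per parameter, 24-48% for at least one, C-index +0.01 to +0.04 in the same patients and −0.01 to −0.02 in new ones.
- Half imaged (about 26-37 events): 8-11%, 28-56%, +0.03 to +0.07, and −0.015 to −0.03.

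**What drives it.** If every test held exactly 5% and tests were independent, the chance of at least one false positive would already be 1 − 0.95^4 = 19% for 4 parameters and 1 − 0.95^8 = 34% for 8. At 7% and 8% it becomes 1 − 0.93^4 = 25% and 1 − 0.92^8 = 49%, close to the simulated 24-48%. Most of the false-positive risk is therefore multiplicity. Few events per term add a little to it and mainly enlarge the C-index optimism.

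Time points and outcomes add tests. Three modalities at three scheduled examinations for two outcomes make 18 tests, and 1 − 0.95^18 = 60% if they were independent. They are not, so the true figure would be lower.

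**The case against.** Section 9.5.4 does not say that all imaging parameters go into one model; entering them one at a time fits the text equally well. On that reading the error of each test stays at about 6-8%: 6.1-6.3% with all 105 imaged and 6.9-7.5% with half, although up to 8.5% was seen when imaging was correlated 0.5 to 0.7 with a prognostic factor. The apparent C-index gain is then at most about 0.01. This stands, and it is why single entry is part of the fix. It does not remove the multiplicity: eight independent single tests at 6% still give 1 − 0.94^8 = 39%.

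The C-index is my yardstick; the plan names none. That also stands, and the undefined notion of usefulness is itself part of the problem.

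The objective is exploratory and funding-dependent, and no primary or secondary conclusion, treatment decision or stopping rule uses these models. This limits the weight of the point but does not make an uncorrected claim of prediction sound.

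A reader might infer that the test level is roughly double the nominal 5%. The documents do not support that as a general statement. It needs about half uptake and about eight parameters entered jointly, and neither figure is stated. A reader might also infer that useless measures will look predictive. Any single null parameter is non-significant in roughly nine runs out of ten or more.

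**Conclusion.** The point holds as a moderate one. Section 9.5.4 has no safeguard separating real imaging signal from chance and same-patient optimism. With 4 to 8 null parameters entered jointly, at least one looks significant in about a quarter to a half of runs, even with all 105 patients imaged. The apparent improvement in discrimination reverses in new patients.

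The size depends on exponential PFS at the design rates, the month-91 cut-off, the assumed adjuster effects, the number of parameters, joint entry and imaging uptake. The last three are not in the documents. OS models would have no more events than PFS models; their number cannot be derived from the plan. The PFS-33 and PFS-38 analyses are not touched.

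**What to change.** In Section 9.5.4:

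1. List the imaging parameters and time points to be tested, and enter one imaging parameter at a time over the clinical factors.
2. Control the false discovery rate over all parameters and time points.
3. Define usefulness as the bootstrap optimism-corrected change in C-index over the clinical model.
4. Label the results hypothesis-generating.

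An optional step is to replace the six adjusters by one clinical score fitted in all enrolled patients. In simulation this held the error at about 4-5.5% for independent or moderately correlated imaging. It fell to 1.6% when imaging correlated 0.7 with a clinical factor and all 105 were imaged, so it can be conservative and lose power.

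The cost is plan wording and some programming, with no new data. Reported imaging effects will look smaller, and false-discovery control gives up some power.

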### **2.3 Rationale for selection by 1p/19q deletion status**

Combined 1p/19q deletion, typically involving the entire chromosome arms at both sites, is a molecular signature of oligodrogiomas, seen in 50%–80% of patients with this histology. 1p/19q co-deletion is also found in 30-50% of oligoastrocytomas and 0-15% of astrocytomas, with an overall frequency of approximately 30% in all adult LGGs [Reviewed in (Sanai, Chang et al. 2011)]. Comparative genomic hybridization, loss of heterozygosity, quantitative microsatellite analysis, and fluorescence *in situ* hybridization are all techniques used to identify tumors with 1p/19q co-deletion. The distinction between a prognostic indicator of clinical outcome regardless of therapy and a predictive measure of response to a particular therapy is very important and 1p/19q co-deletion appears to serve both roles. Its prognostic significance is reflected in longer progression-free survival and more indolent behavior in oligodrogiomas with 1p/19q co-deletion. Its predictive value is reflected in studies that first suggested that 1p/19q co-deletion is a marker of response to PCV chemotherapy and then indicated that 1p/19q co-deleted LGGs also respond favorably to temozolomide [Reviewed in (Sanai, Chang et al. 2011)]. Houillier *et al.* reported that adult LGGs exhibited an objective response rate to TMZ of 66% if 1p/19q co-deletion was present but only 31% if 1p/19q co-deletion was absent (Houillier, Wang et al. 2010). Because of its role as a prognostic factor and predictive marker, paradigms for treatment of adult LGGs incorporate 1p/19q co-deletion status into the decision making process. Therefore, in our study of everolimus for newly diagnosed adult LGGs for whom treatment will be selected by activation of the PI3K/mTOR pathway, we have also chosen to select treatment based on patients' tumor 1p/19q co-deletion status. On this clinical trial, favorable patient with 1p/19q co-deletion will receive single agent everolimus.

---

The less favorable group that lacks 1p/19q co-deletion will be further selected by PI3K/mTOR pathway activation, with pathway activated tumors (reflected in positive phospho-PRAS40 staining) receiving single agent everolimus and pathway non-activated tumors (reflected in negative phospho-PRAS40 staining) receiving dual therapy with everolimus and temozolomide.

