#### **4 Study design**

Treatment for patients with previously untreated LGG will be selected by whether or not their tumor has ATRX loss and/or 1p/19q chromosomal co-deletion. If the tumor is ATRX lost or 1p/19q intact, then patients will be further selected by whether or not their tumor demonstrates activation of the PI3K/mTOR pathway. If activation is present, patients will be treated in Arm 1 with single-agent everolimus at 10 mg daily continuously. If activation is not present, patients will be treated in Arm 2 with combined everolimus and TMZ. Everolimus will be given at 10 mg daily continuously, and TMZ will be dosed initially at 150 mg/m^2/day for 5 days out of a 28-day cycle. If ATRX is intact, 1p/19q co-deletion should be confirmed, or if only 1p/19q co-deletion is available and present, patients will be treated in Arm 3 with single-agent everolimus at 10 mg daily continuously. In all arms, treatment with everolimus will continue for up to 24 cycles, after which patients will be followed with interval MRIs until progression. In Arm 2, TMZ will be stopped after 12 cycles.

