### 9.5.2 Analysis of Primary Endpoints

**33-(38-)month PFS:** Analyses will be performed after all enrolled patients have completed 33 (38) months on study, or whenever the progression status of all patients has been established, whichever comes first. The primary analysis will be based on Kaplan-Meier method. Kaplan-Meier estimates and the associated 95% CIs will be calculated for the 33-(38-)month PFS separately for the three arms. The Cox proportional hazards model will also be used to allow for adjustment of the prognostic factors including age, KPS, and extent of resection.

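### The exploratory imaging models in 9.5.4 appear to give Arms 1 and 2 a single level, leaving treatment and pathway status uncontrolled; arm should enter as three levels

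*Combined protocol and SAP*

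**What the plan says.** Section 9.5.4 plans to "assess the usefulness of these parameters in predicting PFS and OS using Cox regression", and to use logistic regression for response if there are enough responders. Besides the imaging parameter, the models contain KPS, age and extent of resection, together with "time since diagnosis, Arm 1, 2 vs. 3, and initial diagnostic histology scored as oligodendrogloma only vs. those with an astrocytoma component". The reason given is explicit: "The inclusion of these additional variables is to adjust for known or potential confounding risk factors".

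Section 4 defines the two arms that the list appears to group. Both take tumours that are ATRX lost or 1p/19q intact. "If activation is present, patients will be treated in Arm 1 with single-agent everolimus"; without activation, patients go to Arm 2 and receive everolimus with TMZ. Section 2.1 regards pathway activation as predictive of response to mTOR inhibition.

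Under Section 7.2.2 the full imaging examination is optional. It is offered at baseline, at the end of cycles 2 and 6, and at suspected progression.

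**The concern.** The arm entry has the same form as the two-group histology entry beside it, so it reads as Arms 1 and 2 together against Arm 3. Coded that way, the model gives Arms 1 and 2 the same baseline hazard, although they differ in treatment and in a marker that the protocol itself treats as predictive.

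Confounding needs two conditions: the arms must differ in hazard and in imaging values. The protocol's background makes both plausible. Section 7.2 reports vascular imaging measures that fell on everolimus in patients with stable disease, and pre-clinical metabolic changes associated with response to TMZ. The scans at the end of cycles 2 and 6 are taken on treatment. An imaging parameter that merely marks who received TMZ, or whose pathway was activated, could then be reported as an early predictor of PFS or OS.

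**Working it through.** **The plan's own figures.** The documents give no power, event count or error rate for the imaging models. The one design figure, 86% for 35 patients per arm (Section 9.3), reproduces: success at 22 or more of 35 has exact type I error 0.088 at 50% and power 0.865 at 70%. It concerns each arm alone and does not depend on how arm is coded in 9.5.4.

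**Inputs from the documents.** 35 patients per arm (Section 5); median PFS 32.9 months for intact and 37.9 months for co-deleted tumours (9.3); 53 months of accrual and 38 months after the last enrolment (9.5.1), so follow-up runs from 38 to 53 + 38 = 91 months.

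**Assumptions.** Exponential PFS, uniform accrual, no dropout, all patients imaged, and one normally distributed imaging parameter x with SD 1. The Arm 1 hazard is multiplied by the stated ratio and the Arm 1 mean of x is shifted by the stated amount. The true imaging effect is zero. There are 600 replicates per scenario.

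**Models compared**, rejecting when |estimate/SE| > 1.96:
- Lumped: h(t) = h0(t) exp(βx + γ·[Arm 3])
- Three-level factor: h(t) = h0(t) exp(βx + γ1·[Arm 1] + γ3·[Arm 3])
- Strata: h(t) = h0,arm(t) exp(βx)

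Mean estimate of β, and rejection rate:

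| Arm 1 vs 2 hazard ratio | Shift in x | Lumped | Three-level factor | Strata |
|---|---|---|---|---|
| 1 | 0 | +0.004, 5.5% | +0.005, 6.2% | +0.003, 5.7% |
| 1.5 | 0.5 SD | +0.039, 9.0% | +0.005, 8.5% | +0.005, 6.0% |
| 2 | 0.5 SD | +0.054, 6.3% | -0.006, 3.7% | -0.007, 3.8% |
| 2 | 1 SD | +0.110, 18.3% | +0.002, 4.5% | +0.001, 3.8% |

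**Simulation error.** Near 5% it is about 1.96 × √(0.05 × 0.95/600) = 1.7 points. The second row should not exceed the third, because its confounding is weaker, so the mean estimates are the better guide. With d = mean estimate/model SE, the rejection rate is approximately Φ(d − 1.96) + Φ(−d − 1.96):
- Lumped, second row: d = 0.039/0.113 = 0.35, giving 6.4%.
- Lumped, third row: d = 0.054/0.112 = 0.48, giving 7.7%.
- Lumped, fourth row: d = 0.110/0.106 = 1.04, giving 18.0%.
- Three-level factor: |d| is at most 0.006/0.115 = 0.05, giving 5.0%.

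The 8.5% for the three-level factor therefore does not reflect remaining bias. In that run the estimates happened to spread more widely (0.128) than the model SE (0.116).

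**Cost of separating the arms when it is not needed** (equal hazards and no shift, true imaging hazard ratio 1.5 per SD): model SE and power.

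| Imaged per arm | Lumped | Three-level factor | Strata |
|---|---|---|---|
| 35 | 0.126, 91.0% | 0.127, 90.3% | 0.128, 89.8% |
| 20 | 0.171, 74.3% | 0.174, 74.2% | 0.177, 71.2% |
| 12 | 0.229, 49.3% | 0.235, 48.3% | 0.241, 43.7% |

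Strata cost 91.0 − 89.8 = 1.2 points at 35 per arm and 49.3 − 43.7 = 5.6 points at 12. The three-level factor costs 0.7 and 1.0 points. Simulation error on power is 2 to 4 points.

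**The case against.** The wording is compressed and could mean three levels. The stated aim is prediction, not a causal imaging effect. TMZ cannot have altered a baseline scan. The 18% needs a hazard ratio of 2 together with a 1 SD shift, and the documents support neither value. The analysis is exploratory and depends on funding.

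Most of this limits the size of the point without removing it. If three levels were meant, the text still has to say so. Section 9.5.4 itself gives confounder adjustment as the purpose of these covariates. The baseline argument leaves the scans at cycles 2 and 6 exposed to treatment, and pathway status could be related to imaging even at baseline.

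A reader might infer three stronger points, which the documents do not support.

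- **That the Cox model in 9.5.2 also misuses the arms.** That section says "The primary analysis will be based on Kaplan-Meier method", and its estimates "will be calculated for the 33-(38-)month PFS separately for the three arms". It then adds "The Cox proportional hazards model will also be used to allow for adjustment of the prognostic factors including age, KPS, and extent of resection". No arm hazard ratio is promised and no objective compares arms. The sentence leaves open whether the arms are pooled and what is estimated. That is under-specification, not a demonstrated error.
- **That histology repeats the Arm 3 split and should be dropped.** Section 1.1 says most of these tumours are of mixed histology, and Section 2.3 says "1p/19q co-deletion is also found in 30-50% of oligoastrocytomas and 0-15% of astrocytomas", with about 30% co-deleted overall. If half are mixed and 30% of those are co-deleted, mixed tumours supply 0.5 × 0.30 = 0.15 of the 0.30, or half of all co-deleted tumours (before the IDH requirement). These would be scored as having an astrocytoma component, so the overlap is only partial.
- **That stratification is the only remedy, and free.** A three-level factor removes the same bias, and strata lose some power if few patients take the optional imaging.

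**Conclusion.** The point holds for the imaging models only. As most naturally read, the arm term leaves uncontrolled a difference in treatment and pathway status that the covariates are meant to adjust for. The false-positive rate of a 5% test is about 6% to 18% with Arms 1 and 2 lumped, against about 4% to 6% with strata. A three-level factor removes the bias equally, with mean estimates within 0.006 of zero. These rates rest on assumed hazard ratios of 1.5 to 2, assumed shifts of 0.5 to 1 SD and complete imaging. With equal hazards and imaging unrelated to arm, the lumped and separated models perform alike. This is a minor point about an exploratory analysis: the primary Kaplan-Meier analysis, the Cox model in 9.5.2 and the sample size do not depend on it.

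**What to change.** In 9.5.4, replace the arm entry in the covariate list with arm as a three-level factor (two indicators) in the Cox and logistic models. In the Cox models the three arms may instead be strata; Cox strata do not carry over to the logistic model, so the factor is needed there. Keep the histology term. Settle the coding before the imaging data are analysed.

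The cost is one extra parameter and a line of SAP text. If strata are chosen, the power loss is about 1 point with 35 imaged per arm and up to about 6 points with 12, so the factor is the better choice if uptake of the optional imaging is low.

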  - Fasting serum lipid profile (total cholesterol, triglycerides, HDL and LDL) (Day 28 (+/- 7 days) of each even cycle for first 12 cycles, then Day 28 (+/- 7 days) of every 3rd cycle thereafter)
  - Serum pregnancy test: for women of childbearing potential (Day 28 (+/- 7 days) of each cycle).
  - Note the coadministration of everolimus and oral anticoagulants is possible but should be subject to verification of coagulation (INR) once steady state is reached (after one week's treatment).

\*The intent is for these tests to be checked approximately every 28 days for all patients, regardless of treatment delays due to myelosuppression.

- Documentation: All relevant information regarding drug doses, concomitant medications and doses, evaluable lesions with measurements, tumor response, laboratory examinations, and treatment-related toxicities shall be documented in the patient's medical record and flow sheets. Patients will maintain a treatment diary while on therapy. The treatment diary will be initiated on Day 1 of therapy and continue throughout treatment. Treatment diaries will be collected from the patient every 2 cycles for the first 12 months, then every 3 cycles until the patient discontinues therapy.
- Treatment or visit delays for public holidays or weather conditions do not constitute a protocol violation.
- Quality of Life Surveys (optional): 2 surveys will be completed at the end of every 6 cycles while on treatment, (if possible) prior to tumor assessment discussion with the physician.

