### 7.1.3 Follow-up Assessments

- Protocol Completion Assessment:

- After administration of everolimus for two years, patients will have completed study treatment.
- All patients must be observed for safety for 30 days following the last dose of everolimus prior to withdrawal from study. This defines completion of active study participation.
- Physical examination and comprehensive neurologic examination and grading, vital signs including weight, Karnofsky Performance status, all laboratory values, and MRI of the brain must be repeated within 4 weeks of the last day of study only if these have not been evaluated within 14 days, inclusive, prior to the date of withdrawal from study, if patients are able to return to do so. If patients are unable to return for an in-person visit, then they will be contacted by phone to assess toxicity at approximately 4 weeks after that last day of study.
- Quality of Life Surveys (optional): 2 surveys will be completed 1 year post-completion of treatment or at the time of tumor progression if sooner than 1 year post-completion of treatment.
- Long-term Follow-up:
  - After completion of study treatment, patients whose tumors have not progressed will be followed with interval MRIs. These should be done every 4 months (+/- 2 weeks) for 1 year, then every 6 months (+/- 4 weeks) for an additional 2 years, and thereafter as per the discretion of the managing physician.
  - Patients will be followed according to routine clinical practice after removal from protocol therapy or until death, whichever occurs first.
  - Patients removed from protocol therapy for unacceptable adverse events will be followed until resolution or stabilization of the adverse event.
  - Patients off protocol therapy will continue to be followed for PFS and OS only for the purposes of this protocol. If patients are not being seen regularly in clinic, then phone calls for PFS and OS will be made every 6 months.

**Table 7-1** Visit evaluation schedule (note: 1 cycle = 28 days)

Procedures:	Initial Screen	1-month Assessment (by phone)	Assessments every 2 cycles (+/- 7 days unless otherwise noted) for cycles 1-12 of therapy	Assessments every 3 cycles (+/- 7 days unless otherwise noted) for cycles 13-24 of therapy	28 days after completing protocol therapy (+/- 7 days) †	Long Term Follow-Up
Clinical Evaluation: ‡						
Medical History	X					
Vital Signs and KPS ¥	X		X	X	X	
Physical Exam, Neurologic Exam	X		X	X	X	

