### **7.4 Quality of Life Assessment**

Very little data is available prospectively assessing quality of life in patients with low-grade glioma, and it is increasingly appreciated that this is an important aspect of caring for patients with brain tumors. As such, patients on Arms 1 and 3 (those receiving everolimus as monotherapy) will be asked to participate in a quality of life component of the study, filling out questionnaires at enrollment and at the end of every 6 cycles during treatment (at the time of the MRI and clinic visit), then at 1 year post-completion of treatment, again associated with the corresponding MRI and clinic visit, or at the time of tumor progression if that occurs sooner than 1 year post-completion of treatment. Participation in this portion of the study will be voluntary. The survey instruments used will be the FACT-Br and the MDASI-BT, both of which are validated in patients with brain tumors (Weitzner, Meyers, et al. 1995; Liu, Solheim, et al. 2009; Armstrong, Gning, et al. 2009). Whenever possible, patients should fill out the questionnaires at each visit *prior to* meeting with the physician to discuss MRI results.

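### Group-level quality-of-life comparisons lose patients once they progress and make no stated use of the progression survey, so average change may look too favourable, mainly at one year post-therapy

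*Combined protocol and SAP*

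**What the plan says.** **Analysis.** Section 9.5.4 names three times to be compared with baseline: "Data from the end of 12 cycles of therapy, the end of 24 cycles of therapy, and one year post-therapy". The method is stated in one sentence: "Paired T-Tests will be employed to make these comparisons". The next sentence adds that "variability analyses using all available timepoints will be undertaken to evaluate trends within single patients over time", for total and domain scores. The section gives no rule for missing surveys and does not mention the progression survey.

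**Collection.** Section 7.1.2 schedules surveys during treatment: "2 surveys will be completed at the end of every 6 cycles while on treatment". Section 7.1.3 then provides one further survey: "2 surveys will be completed 1 year post-completion of treatment or at the time of tumor progression if sooner than 1 year post-completion of treatment". Section 7.4 and the footnote to Table 7-1 say the same, so the progression survey takes the place of the one-year survey. No later survey is scheduled. Section 7.1.3 also states: "Patients off protocol therapy will continue to be followed for PFS and OS only for the purposes of this protocol".

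**Scope.** QoL is an exploratory objective (Section 3). Participation is voluntary and limited to Arms 1 and 3 (Section 7.4), which is at most 70 patients.

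**The concern.** A paired t-test at a given time uses only patients who have both the baseline survey and the survey at that time. Under the collection schedule, a patient who has already progressed has no scheduled survey at the later times. The patients missing from a comparison are therefore missing because of the event most likely to affect their quality of life, and the mean change describes those still progression-free. The number of missing patients grows with each comparison.

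The survey that records how progressing patients fared is collected, but no named group comparison uses it. A reader of the three mean changes could conclude that quality of life holds steady under everolimus when the means leave out the patients in whom it may not have. Section 7.4 itself notes how little prospective QoL data exist in low-grade glioma, so these results may be cited despite their exploratory status.

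**Working it through.** **Plan's own figure.** The documents give no sample size, power or effect size for QoL, so there is nothing to reproduce there. The PFS design values used below come from Section 9.3: 50% and 70%, with 35 patients per arm and a stated 86%. Requiring at least 22 of 35 successes gives an exact one-sided alpha of 0.088 and power of 0.865, which agrees with the 86%.

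**Inputs.**
- Arm 1 and Arm 3, 35 patients each (Section 5).
- PFS-33 for Arm 1 and PFS-38 for Arm 3, each at p = 0.5 or 0.7 (Sections 3 and 9.3).
- Cycles of 28 days (Section 7.1.2). With 30.44 days per month, cycle 12 ends at 12 × 28 / 30.44 = 11.0 months, cycle 24 at 22.1 months, and one year post-therapy is 34.1 months.
- Assumptions: exponential PFS, full participation, and no survey after progression (the visit sections imply that progression ends the six-cycle schedule but do not say so outright).

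**Share already progressed.** S(t) = p^(t/33) in Arm 1 and p^(t/38) in Arm 3, averaged over the two equal arms. For example, at one year post-therapy with p = 0.5: Arm 1, 0.5^(34.1/33) = 0.489; Arm 3, 0.5^(34.1/38) = 0.537; mean 0.513; progressed 1 − 0.513 = 0.487.

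| Time | p = 0.7: progressed of 70 | p = 0.5: progressed of 70 |
|---|---|---|
| End of cycle 12 | 7.4 (11%) | 13.6 (19%) |
| End of cycle 24 | 14.0 (20%) | 24.6 (35%) |
| One year post-therapy | 20.4 (29%) | 34.1 (49%) |

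Refusals and stopping for toxicity would add to the missing surveys.

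**Bias.** Suppose progression lowers the score by d SD and patients are otherwise alike. The mean over all patients then differs from the mean in progression-free patients by d × (1 − S). The documents give no value for d.

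| Time | d = 0 | d = 0.5 SD | d = 1.0 SD |
|---|---|---|---|
| End of cycle 12 | 0 | 0.05-0.10 | 0.11-0.19 |
| End of cycle 24 | 0 | 0.10-0.18 | 0.20-0.35 |
| One year post-therapy | 0 | 0.15-0.24 | 0.29-0.49 |

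Each range runs from p = 0.7 to p = 0.5.

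**What a model recovers.** A simulation used arm-specific PFS, a within-patient correlation of 0.6 and d = 0.5 SD, with 150 trials per scenario and no change before progression. At one year post-therapy:

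| | True mean change | Paired t-test mean (SD) | Mixed model mean (SD) |
|---|---|---|---|
| p = 0.5 | −0.24 | 0.00 (0.14) | −0.15 (0.13) |
| p = 0.7 | −0.15 | 0.01 (0.12) | −0.08 (0.12) |

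The model included the progression survey, placed at a visit. It recovers 0.15/0.24 = 63% and 0.08/0.15 = 53% of the decline, with no larger spread. The paired t-test's value near zero follows from giving progression-free patients no change. It shows the mechanism and does not predict the trial's result.

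**The case against.** **The progression survey is not discarded.** The all-timepoint analyses in Section 9.5.4 would include it, so a reader who infers that it goes unanalysed goes too far. This stands. Those analyses describe trends in single patients, however, and give no group mean change.

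**Patients are not lost entirely.** Someone who progresses after cycle 12 still counts at cycle 12. Surveys are completed at the MRI visit, if possible before results are discussed, so a patient whose progression is found at the cycle 12 or cycle 24 visit can still supply that pair. Both points stand: the loss is per comparison, and smallest at cycle 12.

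**The one-year comparison might include progression surveys.** Section 7.4 defines a single post-treatment survey, at one year "or at the time of tumor progression if that occurs sooner than 1 year post-completion of treatment". Section 9.5.4 does not say whether its one-year comparison covers that whole slot. If it is meant to, the plan should say so, because the comparison would then mix surveys taken at very different months.

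**The target is debatable.** The objective in Section 3 concerns the course of everolimus treatment, so change among patients still on treatment is a legitimate quantity for the two on-treatment times. The plan does not say that this is the target, and it does not explain the post-therapy comparison.

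**The decline is unknown.** Progression under Section 7.2.3 can be purely radiological, so a lasting fall in quality of life is not implied. This stands, and it is why the size is given as a range that includes zero.

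**Conclusion.** The point holds as a risk of bias in the group means. Each paired comparison is limited to patients with a survey at that time, progression removes patients from later comparisons, and no group comparison is named for the survey taken at progression. At the protocol's own PFS values, 29-49% of eligible patients would have progressed before the one-year comparison. The resulting bias there is zero if progression does not lower the score, 0.15-0.24 SD for a 0.5 SD decline and 0.29-0.49 SD for 1.0 SD. It is clearly smaller at cycle 12. These figures rest on exponential PFS, full participation and assumed declines.

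A reader might infer that deterioration will be hidden. The documents do not support that: they give no decline at progression, and the within-patient analyses would show individual falls. The supported statement is that average change may look too favourable. Severity is low, because QoL is exploratory and optional, covers only Arms 1 and 3, and has no bearing on the primary endpoint.

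**What to change.** In Section 9.5.4:

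1. Replace or supplement the paired t-tests with a likelihood-based repeated-measures mixed model on all collected surveys, including the progression survey. Use actual time, or a pre-stated rule assigning the progression survey to a visit window. The rule is needed because progression can be found at MRIs that fall between the six-cycle surveys. Name a simpler covariance structure in case the unstructured one does not converge: six visits need 6 × 7 / 2 = 21 covariance parameters from at most 70 volunteers.
2. Report the change from baseline to the progression survey as its own comparison.
3. At each time, report the number of patients contributing and the reason for each absence (progression, toxicity, refusal, other).
4. State whether a progression survey can count as the one-year survey.

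The cost is revised analysis wording and slightly more analysis, with no new visits, data or patients. The model brings its own assumption about missing surveys. It reduces the bias but does not remove it, which is why items 2 and 3 belong with it.
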